The proposed study will be the first to provide preliminary data for BEAST among Veterans with elevated anxiety sensitivity reporting functional impairment. The study's first aim will be to adapt an existing brief intervention for anxiety sensitivity for virtual delivery within the VA and augmentation via mobile app to increase homework adherence and treatment gains. The second aim will be to assess the feasibility, acceptability, and usability of BEAST among 15 Veterans with elevated anxiety sensitivity and functional impairment. It is expected that, upon completion, an intervention will be developed that effectively reduces functional impairment due to anxiety through reducing sensitivity to anxiety. Conducting this preliminary study establishes the feasibility, acceptability, and usability of BEAST using pre-existing VHA infrastructure to deliver the intervention (i.e., telehealth, mobile app). This study directly addresses RX-22-003 in that we aim to aid in the recovery from functional impairment in Veterans with elevated anxiety. Based on results of this study, we will propose a fully-powered effectiveness randomized control trial.

List of Abbreviations

BEAST – Brief Enhanced Anxiety Sensitivity Treatment

CBT – Cognitive Behavioral Therapy

CoE – VISN 2 Center of Excellence for Suicide Prevention

CPG – Clinical Practice Guidelines

ITT – Intent-to-treat

MAR – Missing at random

PROMIS – Patient Reported Outcome Measures Information System

Contents

Study Protocol.....	5
Protocol Title: Telehealth CBT to increase engagement in pain treatment.....	5
1.0 Study Personnel.....	5
2.0 Introduction	6
3.0 Objectives	8
4.0 Resources and Personnel	8
5.0 Study Procedures.....	9
5.1 Study Design	9
5.2 Recruitment Methods.....	12
5.3 Informed Consent Procedures.....	13
5.4 Inclusion/Exclusion Criteria.....	Error! Bookmark not defined.
5.5 Study Evaluations.....	14
5.6 Schedule of Assessments	Error! Bookmark not defined.
5.7 Data Analysis	16
5.8 Withdrawal of Subjects	19
6.0 Protection of Human Subjects	19
7.0 References.....	23

Study Protocol

Protocol Title:

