acceptable with minor changes, or c) unacceptable. For each component, our intervention will be considered ready for Aim 2 if at least 4 of 6 clinicians and 4 of 6 veterans meeting eligibility criteria rate it to be acceptable as is and two rate it as acceptable with changes. If any member rates the content as unacceptable, we will meet with these participants individually to discuss why they rated the intervention as such. Experts and stakeholders will again evaluate any component of the intervention that did not meet eligibility criteria after the initial round of review. determine if the change would invalidate the intervention. If so, the team will agree not to make the suggested change. Correspondence with the expert panel will be done via email and virtual meetings. A final meeting regarding the summarized findings from the second round of feedback will be held by the investigative team to finalize the protocol. We will meet with our stakeholders to resolve any disagreements between the investigative team and our stakeholders.

Data analysis for Aim 2: Assess the feasibility, acceptability, and usability of BEAST. We will track the number of Veterans who are recruited per month. We will calculate the percentage of participants who complete the protocol and follow-ups to calculate acceptability. Treatment acceptability will be assessed with the exit interview. Therapist fidelity scores for the individual session will be assessed as the percentage of the content delivered. Interrater reliability for fidelity and competence will be assessed using intraclass correlation coefficients. When incorporating information from the exit interview, raters will provide perspectives, discuss their summarized responses, and reach consensus on different factors (e.g., format, receptivity, feasibility).

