The PI will check the work of the raters and chart the data to further examine the domains, core ideas, and categories that describe the themes. Means and standard deviations for outcomes will be calculated at each assessment, including change scores and correlations across timepoints. We expect large standard errors due to sample size. Distribution of scores will be examined to better evaluate how to analyze these data in future studies. For continuous outcomes, Hedge's g will be calculated to identify a range of the pre-post effect size. Although such calculations are of limited benefit in determining the effect of the intervention, they are helpful in identifying outcomes for which the intervention may be less effective.

For data quality and handling of missing data, descriptive statistics will help identify out of range values and outliers. *The assessment battery* will be considered acceptable if no questionnaires are missing in full in more than 25% of the participants and if reliability is higher than 0.70. *Acceptability of EMA procedures* will be assessed through calculating the percentage of EMA surveys completed as well as completion patterns. BEAST will also be considered feasible and acceptable if $\geq 70\%$ of the EMA sessions are completed by $\geq 80\%$ of participants, consistent with prior rates in studies conducted and reviewed by [name]. Acceptability will also be measured using an adaptation of the PSQ, an 11-item measure that assesses both general program satisfaction (usefulness, acceptability) and perceived utility of program components (face-to-face sessions, EMA/EMI).¹⁸ Finally, an average PSQ general satisfaction score of ≥ 4 (on a 5-point scale) and an average PSQ mobile app score ≥ 4 (on a 5-point scale) will provide support for the feasibility and acceptability of BEAST. The research team and stakeholders will

meet and discuss the intervention regarding benchmarks of acceptability and feasibility as well as the information gathered during the exit interviews.

Power analysis. As this is a pilot trial, we did not conduct a formal power analysis when selecting the sample size. Rather, we used stepped rules of thumb to optimize the overall sample size for the pilot and main effects study.²⁸ Based on these stepped rules of thumb and an expectation of clinical effect sizes in the medium range on primary and secondary outcomes of the RCT, 15 participants is considered adequate.

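### Section 5.7 lets EMA completion confer the label acceptable as well as feasible, gives the satisfaction scores only a supporting role, and does not say what a split result means

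*Combined protocol and SAP*

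**What the plan says.** Section 5.7 sets two kinds of numerical benchmark for BEAST as a whole.

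- **EMA completion.** "BEAST will also be considered feasible and acceptable if" at least 70% "of the EMA sessions are completed by" at least 80% of participants. This is an if-condition, and both labels hang on it.
- **PSQ.** The section goes on: "Acceptability will also be measured using an adaptation of the PSQ". The mean general satisfaction score and the mean mobile app score must each reach 4 on a 5-point scale. Together these "will provide support for the feasibility and acceptability of BEAST".

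Section 5.7 also names measures of acceptability that have no threshold. One is the percentage completing the protocol and follow-ups. Another is qualitative: "Treatment acceptability will be assessed with the exit interview". The research team and stakeholders then discuss the benchmarks alongside the exit interviews.

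Section 5.5 Study Evaluations assigns the measures differently. Feasibility is indexed by retention, average homework completion and the percentage of EMA sessions completed. Acceptability is measured by the PSQ.

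**The concern.** Aim 2 exists to assess feasibility, acceptability and usability, so the rule that attaches these labels governs what the pilot may conclude. In section 5.7 the only benchmark phrased as a condition for calling BEAST acceptable is a compliance measure. The participants' own ratings are supporting evidence. Nothing states whether both must be met, whether one is enough, or how a conflict is reported.

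A conflict is plausible because EMA completion has drivers other than liking the program:

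- Section 5.6 pays $30 per week for EMA, plus $10 per week for completing at least 80% of surveys.
- Section 4.0 has the coordinator contact participants when survey compliance problems arise.
- Section 5.1 has about one week of surveys before the treatment session takes place.

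If the reading is left open until results are known, the choice between a favourable and an unfavourable acceptability conclusion can be made after the fact.

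**Working it through.** **1. Wording compared.**

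| Measure | Section 5.5 | Section 5.7 |
|---|---|---|
| EMA completion | feasibility | condition for feasible and acceptable |
| Retention / completion of follow-ups | feasibility | acceptability (no threshold) |
| Homework completion | feasibility | no benchmark |
| PSQ means | acceptability | support for feasibility and acceptability |

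The two sections do not agree on which measure bears on which label. Section 5.7 supplies no rule for combining them.

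**2. Share of EMA collected before treatment.** The section 5.6 total is $340. The four assessments account for 40 + 40 + 30 + 30 = $140, leaving $200. At 30 + 10 = $40 per week that is 5 paid weeks. This matches section 5.1: about one week at baseline, two after the session, and one after each of two follow-ups. If all five weeks count, about one fifth of the completion measure precedes the session.

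**3. How often the EMA rule passes.** The plan states no pass probability for any benchmark, so there is no figure of its own to reproduce. Inputs from the plan are n = 15 and the 80% share, giving 0.80 × 15 = 12 Veterans. I assume all 15 are in the denominator and that each independently reaches 70% completion with true probability p.

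P(pass) = Σ (k = 12 to 15) C(15, k) p^k (1 − p)^(15 − k)

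At p = 0.8 the four terms are 0.250 + 0.231 + 0.132 + 0.035 = 0.648.

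| True share p | P(EMA rule passes) |
|---|---|
| 0.6 | 0.091 |
| 0.7 | 0.297 |
| 0.8 | 0.648 |
| 0.9 | 0.944 |

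**4. How much the reading matters when ratings are poor.** The plan gives no PSQ standard deviation, so this step rests on assumptions: true means of 3.5 on both scores, SD 0.8, correlation 0.5, a normal approximation, and PSQ results independent of EMA completion. The standard error is 0.8/√15 = 0.207, so the threshold lies (4 − 3.5)/0.207 = 2.42 standard errors above the true mean. Both means then reach 4 with probability 0.0009. Over SDs of 0.6 to 1.0 and correlations of 0 to 0.8, this stays below 0.012.

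With p = 0.8:

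- EMA pass taken as enough: 0.648.
- EMA and both PSQ means required: 0.648 × 0.0009 = 0.0006.

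For a poorly rated program, the unstated rule almost entirely determines the label.

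**The case against.** A reader might infer that meeting the EMA rule alone settles the matter whatever the satisfaction scores show. The documents do not go that far. No sentence says EMA completion is enough on its own or overrides a PSQ failure. The word 'also' is additive: it can introduce one more item in a list to be weighed together, and does not establish that any single benchmark suffices.

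Low ratings also have somewhere to go. Section 5.5 says the exit interview and PSQ will inform refinement with stakeholders. Sections 5.1 and 5.7 return the results to stakeholders after the one-arm trial. Nor is the later trial already committed, as one might infer from the Abstract. Its sentence reads "Based on results of this study, we will propose a fully-powered effectiveness randomized control trial", which ties the proposal to the findings.

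Completion can also be defended as behavioural evidence of acceptability. Section 5.7 uses it that way for the EMA procedures themselves, which is reasonable. Finally, dissatisfied Veterans may complete fewer surveys, which would make a split result less likely than independence implies.

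All of this limits the claim. What remains is that the if-condition names BEAST as a whole and not only the EMA procedures, that it departs from section 5.5, and that a discussion held without a rule does not say which label a split result receives.

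**Conclusion.** The point holds as a defect in a stated rule. Section 5.7 words EMA completion as a condition for acceptability, gives the PSQ only a supporting role, conflicts with section 5.5, and leaves split results undefined. A pilot with low PSQ scores and adequate EMA completion could therefore be labelled acceptable; the documents do not show that it would be.

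The size depends on a quantity the plan does not give. The EMA rule passes with probability 0.09 to 0.94 as the true share of Veterans reaching 70% runs from 0.6 to 0.9, assuming 15 independent participants and no link between completion and satisfaction. The 0.65 at a share of 0.8 is one point in that range, not a predicted rate of wrong conclusions. The PSQ calculation likewise illustrates assumed means and SDs.

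**What to change.** Rewrite the benchmark paragraph of section 5.7 to follow section 5.5:

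- Make the EMA benchmark (70% of sessions by 80% of participants) a criterion for feasibility, presented with retention and homework completion.
- Make the two PSQ means of 4 or more the criterion for acceptability, read with the exit interviews.
- Report each benchmark separately with its observed value.
- State that an EMA pass with a PSQ fail is reported as feasible, acceptability benchmark not met, and the reverse likewise.

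The sentence on acceptability of the EMA procedures can stay, since it concerns the procedures and not BEAST. No formal gate on proposing the later trial is needed for this point.

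The cost is one paragraph, settled before results are seen, with no new data collection. The small downside is that a favourable overall declaration becomes less likely.

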5.8 Withdrawal of Subjects

Participants who wish to withdraw may do so at any time without affecting their medical care or participation in any other study. Participants will be informed of any new information throughout the duration of the study which may affect their condition or influence their willingness to continue in this study. Finally, based on decisions made by the Principal Investigator, participants may be taken out of the study because of unanticipated circumstances such as extreme distress. That is, they may be withdrawn from the study if we judge that participating is not in their best interest.

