5.0 Study Procedures

5.1 Study Design

Aim 1 Study Design

Study sample and Screening: We will recruit 6 therapists with experience in telehealth and CBT treatment of Veterans with anxiety and 6 Veterans who meet study eligibility for Aim 2 through the Canandaigua, NY VA.

Assessments and Intervention: Stakeholders (masters-level or higher therapists and Veterans meeting eligibility criteria) will be enrolled following consent. Separate consent forms have been developed for the initial session and the second session. The framework for BEAST exists and will be refined based on feedback received from stakeholders. BEAST comprises two components: face-to-face virtual sessions delivered via telehealth and EMI based on the skills acquired in session, delivered via mobile app. Stakeholders will be asked a series of open- and close-ended questions about the intervention (see Appendix) using an evidence-based expert consensus method for refining the intervention and tailoring the protocol for Veterans. Stakeholders will evaluate the final product after we have completed the one-arm trial and compiled and organized the exit interview information. Final modifications will be incorporated again through seeking consensus with stakeholders.

The study team will work with the Center for Mobile Applications Research Resources & Services (CMARRS) to refine the mobile app and therapist dashboard that will be used to deliver the EMA/EMI components of the intervention. The initial development will occur with the study team using the Mobile App Rating Scale, a multi-dimensional scale assessing an app's engagement, functionality, aesthetics, information, and subjective quality as well as items assessing the perceived impact of the app on the target audience's knowledge, attitudes, intentions to change and likelihood of changing.⁴⁰ Ratings across scales range from 1 ("inadequate") to 5 ("excellent"). We will proceed with our app once it receives consensus scores of 4 or higher across all scales among the study team. In the unlikely event that consensus ratings are not achieved, we will resolve through a study team meeting and a simple majority being used to select consensus.

Veteran participants will receive compensation for their participation in the study. The compensation amount will be based on the following:

Prior to Pilot Study	\$50
Completion of Pilot Study	\$50

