Assessments and Intervention: Veterans will be enrolled following informed consent. Veterans will next complete the baseline assessment. At the baseline assessment, Veterans meet with the Project Coordinator by phone or virtually to complete a consenting process, guidance on the video software being used, and set-up and guidance of the mobile app. Research team member will reach out to the Veteran the following day to address any issues with using the app. Veteran will complete assessment surveys for approximately 1 week. At the baseline appointment, participants will be scheduled to receive the face-to-face virtual intervention followed by two weeks of EMA/EMI via mPRO. At the end of the two weeks, Veterans will complete a post-intervention assessment appointment. Follow-up assessment appointments will be completed at the 1-month and 3-month follow-ups. The post-intervention assessment includes an exit interview for participants to provide additional feedback regarding acceptability of the intervention. The research staff will read the measures to the Veteran who will verbally provide their answers; we have found this improves data reliability and completeness immensely compared to mailing packets/sending survey links.

BEAST contains two components: First, there is a single session **face-to-face virtual intervention** delivered by the counselor or therapist, delivered via VA Video Connect software. Second, a **mobile app (mPRO) is used for EMA and to deliver EMI components.**

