Face-to-face session. The face-to-face session is a one-hour manualized intervention that uses interactive content to enhance participant learning of critical intervention components. The session includes 1) psychoeducation regarding the role of anxiety sensitivity in exacerbating anxiety sensations, 2) practice identifying and challenging maladaptive thoughts about anxiety, and 3) an IE activity. Psychoeducation is first provided, focusing on the body's alarm system with a goal of normalizing bodily sensations associated with anxiety. Following psychoeducation, the participant and therapist discuss sensations the participant experiences when they are anxious and the thoughts about these sensations that serve to maintain them. The participant and therapist explore challenges to any strongly held beliefs about the danger of anxiety sensations. Finally, the IE consists of: repeated trials of hyperventilation given evidence that this challenge is among the most anxiety-provoking for individuals with panic disorder and our experience using this IE exercise in prior RCTs,¹⁰⁻¹² as well as repeated trials of another selected interoceptive exposure activity. To aid in personalization, Veterans assist in choosing 3 **key takeaways** that summarize what they learned from the intervention regarding anxiety sensations as benign. Common summaries from past participants include: *Anxiety sucks, but it is harmless; I've been anxious before, no big deal!* These summary phrases are incorporated into the EMI. Participants are also asked to complete one set of IE exercises daily for the next two weeks.

EMA. EMA will be collected from baseline to post-intervention and for one week after completing each follow-up. This measurement burst design allows for ratings of functional impairment and anxiety to be calculated disambiguated from state level influences. In our future RCT, this will provide additional power to explore the mechanisms at play. Consistent with best-practice recommendations¹³ we will employ a mixture of *fixed time-based sampling*, *experience sampling*, and *event-based sampling* strategies. In the morning, participants will receive a fixed time-based survey that will include a short battery of questions that will take approximately 2

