COVID-19 Impact Battery (CIB) Worries.²⁵ An 11-item scale measuring distress and worry due to the COVID-19 pandemic.

COVID-19 Impact Battery (CIB) Behaviors.²⁵ A 12-item scale assessing avoidance behaviors in relation to the COVID-19 pandemic.

Depressive Symptom Index – Suicidality Subscale (DSI-SS). A 4-item measure assessing suicidality within the previous two weeks.

Demographics. At screening, we will assess participants' gender, age, educational background, employment, income, race, ethnicity, marital status, and socioeconomic status.

Exit Interview. The exit interview will assess overall impressions, impact of treatment, relationship with the therapist, and ways to improve the treatment. Acceptability will be measured using an 11-item adaptation of the Program Satisfaction Questionnaire (PSQ) that assesses both general program satisfaction (usefulness, acceptability) and perceived utility of program components (psychoeducation, EMA/EMI schedule).¹⁸ The exit interview and PSQ will inform further refinement of the intervention as needed with our stakeholders. The exit interview will also consist of a number of open ended questions, including prompts to ask for more information, to collect worthwhile feedback on the study procedures, intervention, and their overall feelings toward the intervention.

EMA Measures:

*State Short Scale Anxiety Sensitivity Inventory; SSAS*²⁰: measures anxiety sensitivity.

*State Penn State Worry Questionnaire; PSWQ*⁵¹: measures anxious apprehension.

State Anxiety Depression Distress Inventory-27; ADDI-27: measures anxious arousal

The PSWQ and ADDI-27 have been validated as measures of general anxious apprehension and anxious arousal, respectively, reflecting the two core anxiety dimensions underlying anxiety disorders.^{26,27} Participants will also rate their impairment across functional domains using the

12-item WHODAS 2.0. Visual analog scale (VAS) ratings from 1-100 will be used to assess anxiety, stress, and depression four times daily. ASI-3 items, revised to capture in-the-moment beliefs, will also be completed. Three items will be randomly selected from an ideographically developed pool of items the participant rates as impacting them “much” or “very much.” Thus, the pool of items to be drawn to potentially deliver EMI will differ by individual.

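### Section 5.8 describes removal from the whole study for extreme distress but no stop of BEAST alone, so a removal before the post-intervention visit can lose the exit interview, the PSQ and three assessments

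*Combined protocol and SAP*

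**What the plan says.** Section 5.8 leaves removal to the PI: "participants may be taken out of the study because of unanticipated circumstances such as extreme distress". It then restates the rule at the same level: "they may be withdrawn from the study if we judge that participating is not in their best interest". Both sentences concern the study, not the intervention.

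The timetable is in section 5.1 (Aim 2 Design). One telehealth session is followed by two weeks of app-based assessment and prompts. Then: "At the end of the two weeks, Veterans will complete a post-intervention assessment appointment". On content: "The post-intervention assessment includes an exit interview for participants to provide additional feedback regarding acceptability of the intervention". Assessments at 1 and 3 months follow.

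BEAST is active from the session to that visit. The session includes "repeated trials of hyperventilation given evidence that this challenge is among the most anxiety-provoking for individuals with panic disorder". Afterwards, "Participants are also asked to complete one set of IE exercises daily for the next two weeks".

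Section 5.5 describes an 11-item PSQ under the exit interview and states the purpose of both: "The exit interview and PSQ will inform further refinement of the intervention as needed with our stakeholders". Section 5.1 (Aim 1) adds: "Stakeholders will evaluate the final product after we have completed the one-arm trial and compiled and organized the exit interview information". Section 5.7 names the exit interview as the means of assessing treatment acceptability. It counts mean PSQ scores of at least 4, for general satisfaction and for the app, as support for feasibility and acceptability.

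**The concern.** A pilot meant to refine an intervention needs to hear from the people who found it hardest to tolerate. Section 5.8 could be triggered during the two weeks in which the exposure exercises are being done, before any exit feedback has been collected. The protocol itself expects that some participants may be distressed (section 6.0, Protection Against Risk).

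If the PI follows section 5.8 as written, the exit interview and PSQ of that Veteran can go missing, and for a reason related to what they would have said. Refinement and the acceptability summary would then rest on those who tolerated BEAST better. The individual's later outcome scores would be lost too.

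The gap matters mainly in this window. Before the session there is no BEAST experience to report. After the post-intervention visit no BEAST component is scheduled, so there is nothing left to stop.

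**Working it through.** **Inputs.** Planned Aim 2 sample: 15 (sections 3.0 and 5.2). Assessments: baseline, post-intervention, 1-month, 3-month (section 5.6). Payments: \$40, \$40, \$30, \$30, plus \$30 per week of app data and \$10 per week for completing at least 80% of surveys; total \$340 (section 5.6).

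**1. Reproducing the plan's figure.** The four assessments pay 40 + 40 + 30 + 30 = \$140. App weeks: 1 at baseline + 2 after the session + 1 after each of 2 follow-ups = 5. These pay 5 × (30 + 10) = \$200. The total is 140 + 200 = \$340, as stated, so the schedule has been read correctly.

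**2. Loss per Veteran removed between the session and the post-intervention visit.**
- Assessments: 4 − 1 = 3 remain, and 3/4 = 75% can be lost.
- The first of the three is the only visit stated to contain the exit interview.
- Share of planned exit interviews: 1/15 = 6.7%; for two removals, 2/15 = 13.3%.
- Share of all post-baseline assessments: 3/(3 × 15) = 3/45 = 6.7%.

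**3. What the plan's other measures would show.**
- Completion: 14/15 = 93.3% after one removal, 13/15 = 86.7% after two.
- Battery benchmark (no questionnaire missing in full in more than 25%): 3/15 = 20.0% passes and 4/15 = 26.7% fails, so up to three removals alone would not breach it.
- App benchmark (at least 70% of surveys completed by at least 80% of participants): with 7 + 14 + 7 + 7 = 35 scheduled days as the denominator (an assumption), removal on day 14 after the session leaves at most 21/35 = 60%, so the removed Veteran fails. The benchmark is still attainable after three removals (12/15 = 80%) but not after four (11/15 = 73.3%).

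**4. Illustration with assumed values.**
- PSQ: if 14 Veterans average exactly 4.0 and the removed one would have scored 1 to 2, the mean over 15 is (56 + 1)/15 = 3.80 to (56 + 2)/15 = 3.87.
- Chance of at least one removal, 1 − (1 − p)^15: 26% for p = 2%, 54% for p = 5%, 79% for p = 10%.

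The documents give neither a removal rate nor expected PSQ scores. These figures show only what could happen.

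**5. Is a lesser step written elsewhere?** None was found.
- Section 6.0 (Adverse Events) lets the PI change the protocol or make other changes to reduce risk, but after serious events or protocol deviations and at study level.
- Sections 5.6 and 6.0 pay non-completers for the parts they finished and do not mention further contact.
- Section 4.0 covers contact over app compliance.

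**The case against.** The strongest reply is that silence is being read as a rule. Section 5.8 is permissive and bars neither a lesser step nor a closing call. That stands: a reader might infer that the protocol requires full removal or forbids later contact, and it does neither. The point is that staff have no written lesser option.

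A reader might also infer that these Veterans would vanish from the data. They would not:
- sessions are recorded, coded and reviewed in supervision (section 4.0);
- app ratings and exercise tracking exist up to removal (sections 5.1 and 5.5);
- removal lowers the completion percentage, itself a stated acceptability measure (section 5.7);
- section 5.7 commits to CONSORT reporting.

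All of this stands. None of it supplies the Veteran's own account of what went wrong, which is what the exit interview is for.

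A third inference, that removal leaves the Veteran without a safety net, is not supported. The crisis procedures apply, the crisis-line number is given at baseline as well as at follow-up, and the PI tracks all negative outcomes (section 6.0). What is lost is repeat contact.

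Finally, ending every procedure can be right. Section 6.0 says that assessments, as well as therapy, may cause distress. That is a reason to keep full removal available, but not to make it the only step described. Consent pages and the written emergency procedures were not available for review and might cover part of this.

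**Conclusion.** The point holds as a modest, inexpensive improvement. Section 5.8 describes only study-level removal for extreme distress. Used between the session and the post-intervention visit, it can cost that Veteran's exit interview, PSQ and three of four assessments. Each case is 6.7% of a sample of 15, and the loss is selective.

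The conclusion rests on two readings: that removal from the study ends assessments, and that the PSQ is given with the exit interview, as section 5.5 describes it. The number of removals to expect is unknown, so the size of any bias in PSQ means or change scores cannot be estimated. It would go too far to say that the satisfaction benchmark would be met wrongly: the 3.80 to 3.87 illustration depends on assumed scores, and the PSQ mean is one supporting criterion among several. The study is a single-arm, descriptive pilot, so no hypothesis test is at stake.

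**What to change.** In section 5.8:

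1. Separate stopping BEAST (the session, the app prompts, the interoceptive exercises) from leaving the study. Keep the PI's discretion to do either.
2. Unless the Veteran withdraws consent or the PI judges contact itself harmful, offer a Veteran stopped for distress a voluntary exit interview and PSQ and the assessments already scheduled. Allow a reduced form, for example the DSI-SS and an adverse-event question, with the crisis-line number repeated.
3. Report the number stopped for distress beside the PSQ means and change scores, with their last observed scores.

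The cost is one paragraph and a check that the consent wording agrees. The three contacts are already scheduled, with 40 + 30 + 30 = \$100 per Veteran already allotted. The downside is a few short calls, some refusals and possible assessment-related distress, limited by voluntariness and the PI's override.
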